CHD	CORONARY HEART DISEASE
CRC	CLINICAL RESEARCH COORDINATOR
CRF	CASE REPORT FORM
CVA	CEREBROVASCULAR ACCIDENT
CVD	CARDIOVASCULAR DISEASE
DGMC	DAVID GRANT MEDICAL CENTER
DUHS	DUKE UNIVERSITY HEALTH SYSTEM
DUMC	DUKE UNIVERSITY MEDICAL CENTER
EMR	ELECTRONIC MEDICAL RECORD
FBG	FASTING BLOOD GLUCOSE
FRS	FRAMINGHAM RISK SCORE
GCP	GOOD CLINICAL PRACTICES
GRC	GENETIC RISK COUNSELING
HbA1c	HEMOGLOBIN A1C
HC	HEALTH COACHING
HDL	HIGH DENSITY LIPOPROTEIN CHOLESTEROL
HIPAA	HEALTH INSURANCE PORTABILITY AND ACCOUNTABILITY ACT
HT	HEIGHT
ID	IDENTIFIER
IRB	INSTITUTIONAL REVIEW BOARD
LDL	LOW DENSITY LIPOPROTEIN CHOLESTEROL
MC	MCCLELLAN
MI	MYOCARDIAL INFARCTION
NCI	NATIONAL CANCER INSTITUTE
PCP	PRIMARY CARE PROVIDER
PHI	PROTECTED HEALTH INFORMATION
PI	PRINCIPAL INVESTIGATOR

Genetic Risk Testing and Health Coaching for CHD and T2D
Duke IRB# Pro00039569 NCT01884545

RCT	RANDOMIZED CONTROL TRIAL
REDCap	RESEARCH ELECTRONIC DATA CAPTURE
SAE	SERIOUS ADVERSE EVENT
SBAS	STANFORD BRIEF ACTIVITY SURVEY
SBP	SYSTOLIC BLOOD PRESSURE
SRA	STANDARD RISK ASSESSMENT
T2D	TYPE 2 DIABETES
TAFB	TRAVIS AIR FORCE BASE
TC	TOTAL CHOLESTEROL
TRIG	TRIGLYCERIDE
UAE	UNEXPECTED ADVERSE EVENT
USAF	UNITED STATES AIR FORCE
WT	WEIGHT

Table of Contents

Background and Rationale.....	1
Trial Objectives	1
Patient Selection	2
Registration Procedures.....	4
Study Design.....	4
Adverse Events.....	14
Data Reporting/Regulatory Considerations.....	16
Statistical Considerations.....	18
Protection of Human Subjects.....	21
Risk/Benefit Assessment.....	23
References	24
Appendices	25

1. Background and Rationale

Military personnel are not exempt from increasing rates of overweight and obesity; or the associated rising burden of coronary heart disease (CHD) and type 2 diabetes (T2D) seen in the U.S. population. Innovative and clinically feasible approaches to address these chronic disease risks are needed, particularly those that motivate and support sustainable, risk-reducing health behaviors.

Risk assessment, historically based on clinical risk factors alone (e.g., blood pressure, cholesterol) is a central aspect of preventive care. In recent years, however, over one hundred genetic markers associated with increased risk for CHD have been described [1], and for T2D there are approximately 40 well-validated markers associated with increased risk [2]. While risk for both conditions remains modifiable with lifestyle changes such as diet and exercise [3], the feasibility and utility of integrating genetic risk information into primary care patients' global risk assessment for common chronic diseases remains unknown.

In addition, pairing a behavioral intervention with the provision of genetic risk information may be even more effective than the same intervention with more familiar clinical risk information alone [4]. This study will examine the impact of providing genetic CHD and T2D risk information, with or without a supportive behavioral intervention, on promoting risk-reducing behaviors and improving clinical outcomes.

2. Trial Objectives

In short, using a 4-group (2X2) randomized controlled trial (RCT) design, this study will determine whether incorporating multiple-marker genetic testing into risk counseling for CHD and T2D [5], coupled with a health coaching intervention will lead to greater changes in physical fitness, health behaviors, risk status and clinical outcomes in active-duty Air Force (ADAF), beneficiaries, and retiree patients. We will address the following task objectives or primary aims:

1. Determine the main and interactive effects of multiple-marker genetic risk information incorporated into standard CHD and T2D risk counseling (Standard Risk Assessment, or SRA) and an established, structured telephonic health coaching (HC) intervention on health behavior change (diet, exercise habits, smoking cessation) over 12 months, with a focus on ADAF, beneficiaries, and retiree patients.

Genetic Risk Testing and Health Coaching for CHD and T2D

Duke IRB# Pro00039569 NCT01884545

2. Determine the main and interactive effects of genetic risk information incorporated into standard CHD and T2D risk counseling and a telephonic HC intervention on clinical outcomes (fasting blood glucose (FBG), systolic blood pressure (SBP), body mass index (BMI), Low-density lipoprotein cholesterol (LDL), triglycerides (TRIG), total cholesterol (TC), AF composite fitness scores, Framingham risk score (FRS), Diabetes risk score.

Secondarily, we will determine the effects of potential mediators of primary outcomes, including perceived risk, patient activation, stages of change for behaviors of interest, and psychosocial risk factors for CHD and/or T2D (depression, unmanaged stress, and social isolation).

3. Patient Selection

3.1. Target Population

The study population includes adult patients, 18-65 years of age, followed at AF primary care clinics with at least one risk factor for either CHD or T2D as defined in the inclusion criteria.

3.2. Inclusion Criteria

Patients will be eligible for inclusion in this study only if all of the following criteria apply:

1. Age 18 to 65 years
2. Willingness and ability to provide informed consent
3. Have an active email address and internet access
4. Physical exam in the last 6 months with the following documented evaluations in EMR:
 - a. Blood pressure
 - b. Height and weight
 - c. Fasting blood glucose or Hemoglobin A1C (HbA1c)*
 - d. Lipid panel (TC, LDL, HDL, TRIG)

with at least one of them outside of the normal ranges defined as:

- i. $BMI \geq 25 \text{ kg/m}^2$ ($BMI = \text{weight} [\text{kg}] / \text{ht} [\text{m}]^2$)
- ii. $FPG > 100 \text{ AND } \leq 125 \text{ mg/dL}$

Genetic Risk Testing and Health Coaching for CHD and T2D

Duke IRB# Pro00039569 NCT01884545

- iii. HbA1c $> 5.7\% \leq 6.4\%$
- iv. SBP ≥ 130 mmHg
- v. TC ≥ 200 mg/dL
- vi. TRIG ≥ 150 mg/dL
- vii. LDL ≥ 129 mg/dL

* If a Fasting blood glucose or Hemoglobin A1C (HbA1c) and lipid panel are - documented within the last 6 months they will also be used to determine eligibility as defined above. If either of these tests have not been done in the last 6 months as part of standard care, they will be drawn after consent, either within 4 weeks prior to the baseline visit or at the baseline visit to ensure that the results are available during the baseline visit to confirm eligibility.

3.3. Exclusion Criteria

A patient will **not** be eligible for inclusion in this study if any of the following criteria apply:

1. Projected deployment in the upcoming 6 months ;
2. Diagnosed T2D;
3. Diagnosed CHD (MI, or documented CHD);
4. Inability to ambulate or participate in physical activity;
5. Serious chronic disease related complications or conditions that could significantly affect study outcomes [currently treated cancer, renal failure, cardiovascular accident (CVA) with residual effects on functioning];
6. Current participation in another research study ;
7. Spouse, partner or other household member already participating in this study protocol.

The cardio-metabolic risk factors used for inclusion are those identified by the FRS and national guidelines (National Cholesterol Education Program, AHA, ADA). Because we are targeting those at risk for CHD and/or T2D, participants must have at least one factor in the risk ranges listed. Patients with diagnosed CHD or T2D are excluded because this study is targeted toward prevention of these conditions in those at risk. Those with physical activity limitations or other serious co-morbidities are excluded due to potential effects on participation and study outcomes. The age limit of 18-65 years was designated as much of the risk of T2D or CHD in older adults is due to

age; not modifiable risk factors. Therefore, many intervention studies aimed at risk reduction limit participation to those at age 65 or younger.

3.4. Inclusion of Minorities

Adult patients of all races and ethnic groups will be considered for study participation.

4. Registration Procedure

All patients who have signed informed consent and met the eligibility criteria will be registered in the Research Electronic Data Capture (REDCap) system and will be issued a study specific ID number.

4.1. Institutional Registration

Patient registration at each study site/institution will be conducted according to the institution's established policies. Prior to registration, patients will be asked to sign and date an Institutional Review Board (IRB)-approved consent form.

4.2. Informed Consent

Authorized study personnel should fully explain the scope of the study to each patient before obtaining informed consent. When obtaining informed consent, study personnel should:

First: Confirm that the patient is a potential candidate for study participation.

Next: Obtain dated and signed informed consent document.

Finally: Confirm that the patient is eligible as defined in Sections 3.2 and 3.3 (Inclusion/Exclusion Criteria).

5. Study Design

This trial will recruit primary care patients at David Grant Medical Center (DGMC) that have at least one risk factor for CHD or T2D. Enrolled subjects will be randomized to one of four groups:

1. Standard Risk Assessment (SRA) only;
2. SRA plus Health Coaching (SRA+HC);
3. SRA plus Genetic Risk Counseling (SRA+GRC); ***or***
4. SRA+HC+GRC

The primary outcomes of this study are behavioral (diet and exercise/fitness), collected at 6 weeks, and 3, 6 and 12 months. At 12 months, clinical outcomes will be measured at the clinic (blood pressure, weight, and waist circumference). And at 12 months, clinical outcomes will be documented from the electronic medical record (EMR) (glucose, lipid panel, change in risk status, AF fitness scores*) from the subjects' annual visit results.

*Note: AF fitness scores are provided following required annual fitness evaluations for all ADAF only (not beneficiaries, retirees) and are age and gender based. The variables considered with points for level of performance in each category are: Cardiorespiratory endurance (run time); Body composition (abdominal circumference); and Muscle fitness (push-ups). A composite score derived from adding points in all categories must be >75. Ranges are defined for Unsatisfactory; Satisfactory and Excellent.

5.1. Expected Enrollment

Total of two hundred fifty (250) subjects will be enrolled in two primary care clinics, at two sites as follows:

1. David Grant Medical Center ,Travis Air Force Base, Solano, California
2. McClellan Outpatient Satellite Clinic, McClellan Air Force Base, Sacramento County, CA

5.2. Recruitment

Ascertainment of potential subjects will be obtained by physician referral, patient self-referral or EMR chart review (Appendix I. and J.) The study coordinator will mail a letter, signed by the subjects' primary care physician, to those individuals identified by EMR chart review, introducing the study. After 2 weeks, the CRC will follow-up with a brief phone call to assess subjects' interest in study participation. (Appendix G. and H.). If the potential subject is interested in participation, consent and baseline visit will be scheduled. Patients identified by physician referral may be consented at time of physician referral or contacted later by phone to arrange consent and/or baseline visits. For

Genetic Risk Testing and Health Coaching for CHD and T2D

Duke IRB# Pro00039569 NCT01884545

self-referred patients the initial phone conversation will be followed by consent/baseline visit in the clinic. Since a major target population for this study is ADAF, beneficiaries, and retiree patients, we will be placing flyers/advertisements/recruitment staff in locations on base to reach this audience including gymnasiums, annual fitness evaluation centers and annual exam clinics on base.

5.3. Schedule of Events

5.3.1. Visit Overview

Baseline visit:

[figure not shown]
Informed consent will be obtained and documented. Inclusion and exclusion criteria will be verbally verified with participant and date of consent will be documented on the Case Report Form (CRF, Appendix A.). Height, weight, waist circumference, and blood pressure will be measured by CRC and documented on CRF. Refer to section 5.3.2. Study Specific Tests and Procedures for methods of obtaining height, weight, waist circumference, and blood pressure.

Most recent lab results (FBG or HbA1c, TC, TRIG, HDL, LDL, last PHA,) and current medications will be obtained from the EMR. Last fitness score will be obtained from a separate database, outside of the EMR. Participants who are not active duty will not have PHA with fitness scores. All variables measured directly or obtained from EMR will be entered into REDcap by CRC. Subjects randomized to the two genetic arms will have blood collected and sent for testing at Duke University Clinical Molecular Diagnostics Laboratory. Female subjects will be asked if they are currently pregnant and this will be documented (Note: the purpose of collecting pregnancy information is to account for potential confounders later in analysis; not for exclusion criteria). Participants will be registered in REDCap database. They will complete the baseline survey during their clinic visit (at a clinic computer).

Genetic Risk Testing and Health Coaching for CHD and T2D

Duke IRB# Pro00039569 NCT01884545

Fig.1. Study Schema

Genetic Risk Testing and Health Coaching for CHD and T2D

Duke IRB# Pro00039569 NCT01884545

Randomization:

Randomization will take place to *one* of the following:

1. Standard Risk Assessment (SRA) only;
2. SRA plus Health Coaching (SRA+HC);
3. SRA plus Genetic Risk Counseling (SRA+GRC); *or*
4. SRA+HC+GRC

Random assignments will be generated using a standard random number generator with uniform distribution to the four groups by the Clinical Genomics Study Unit (CGSU) data manager. The research staff (CRC at site) will use this randomization schema to inform participants of their group assignment.

Follow up visits:

6-week and 3-month – At 6 weeks and 3 months after the baseline visit, participants will be asked to complete selected surveys online (Table 1). The 6 week survey must be completed after the counseling visit and before Health Coaching begins.

6-month – Six months from the baseline visit, participants will return to the clinic to have weight, BP and waist circumference measured (same procedures as baseline visit). Medications will be reviewed and AE's assessed.

Female subjects will be asked if they are currently pregnant and this will be documented.

They will also complete the required surveys as listed, either before their scheduled visit or during their visit at the clinic.

12-month- Twelve months from the baseline visit, participants will return to the clinic for a final visit to have weight, BP and waist circumference measured (same procedures as baseline visit). Medications will be reviewed and AE's assessed.

Lab values from the EMR will be documented for fasting glucose, TC, HDL, LDL, TRIG CRC will check in EMR prior to each subject's 12-month visit. If lab values as stated above are not available from the last 6 months of study participation , then a lipid panel (TC, HDL, LDL, TRIG) and either a FBG or HbA1c will be ordered. Female subjects will be asked if they are currently pregnant and this will be documented.

They will also complete the required surveys as listed, either before their scheduled visit or during their visit at the clinic.

Window of ±one week were allowed for all follow up visits. In order to maximize power and considering

Genetic Risk Testing and Health Coaching for CHD and T2D

Duke IRB# Pro00039569 NCT01884545

recent findings on the stability of metabolic clinical markers absent behavior change, statistical analyses will employ extended inclusion windows for study time-points. Statistical analyses will include: +/-3 weeks for the 6 week survey, +/-7 weeks for the 3 month survey, and +/-11 weeks for the 12 month survey.

Table 1.

STUDY VISITS	GROUP 1	GROUP 2	GROUP 3	GROUP 4
	Risk Assessment Only	Risk Assessment +Health Coaching	Risk Assessment +Genetic Test	Risk Assessment +Health Coaching +Genetic Test
CONSENT**/ BASELINE VISIT	Consent Survey Height, Weight, Waist, BP	Consent Survey Height, Weight, Waist, BP	Consent Survey Height, Weight, Waist, BP Blood Draw	Consent Survey Height, Weight, Waist, BP Blood Draw
RISK ASSESSMENT VISIT	Risk Assessment	Risk Assessment	Risk Assessment + Genetic Result	Risk Assessment + Genetic Result
6 WEEK SURVEY	On-line survey	On-line survey	On-line survey	On-line survey
3 MONTH SURVEY	On-line survey	On-line survey	On-line survey	On-line survey
6 MONTH VISIT	Survey Weight, Waist, BP Meds, Assess AE	Survey Weight, Waist, BP Meds, Assess AE	Survey Weight, Waist, BP Meds, Assess AE	Survey Weight, Waist, BP Meds, Assess AE
12 MONTH VISIT	Survey Weight, Waist, BP Meds, Assess AE, Labs	Survey Weight, Waist, BP Meds, Assess AE, Labs	Survey Weight, Waist, BP Meds, Assess AE, Labs	Survey Weight, Waist, BP Meds, Assess AE, Labs

**Consent may be obtained at a separate visit if HbA1c and/or lipid panel labs need to be performed for eligibility confirmation. If done separately Baseline visit should occur within 4 weeks of consent.

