Samples will be sent to Duke University Clinical Molecular Diagnostics Laboratory, which is CLIA-certified. DNA extraction will be performed as well as real time PCR allelic discrimination assays for RS7903146, RS1801282, RS5219, and RS10757274 (Appendix P.). Results (genotyping of alleles for SNPs of interest) will be returned by subject studyID number to the site research staff for entry into the REDCap database. Remaining blood samples will be retained by the lab until the end of the study, at which time they will be discarded.

Standard Risk Assessment (SRA) for CHD and T2D (need to take place no later than 4 weeks post randomization)

The SRA has been developed for this study based on the Framingham risk assessment and other known risk factors for CHD and T2D. The SRA consists of: FBG, age, gender, BMI, total cholesterol, HDL, BP, family history (number of first-degree relatives who have CHD (and age at diagnosis) or T2D, self-reported), and smoking (self-reported). A Framingham Risk Score and Diabetes Risk Score will be calculated for each patient along with other well-validated CHD and T2D risk factors, and all will be reviewed at the risk counseling visit. This method of presenting genetic risk data to patients has successfully been used for over 400 clinical study patients to be used by the provider (Appendix K., L., M., N.).

Health Coaching(HC) Intervention. Upon completion of their individual SRA Visit, participants in the two groups that include health coaching will be assigned to a trained health coach for a period of 5 months (n=200). At the SRA, the participant will fill out a “Current & Desired States Form” (Appendix C.). Then the participant will be given a folder containing information about what HC is, how the calls will be structured, and preparation materials for the calls (Appendix E.). An initial telephone call (60-75 minutes in length) with the coach will consist of a discussion on the role of the health coach and participant, the logistics of the sessions, and a discussion about the participant’s self-assessment of health perceptions and goals. This self-assessment creates the foundation for the personalization of the behavioral intervention. From this point, the

Genetic Risk Testing and Health Coaching for CHD and T2D

Duke IRB# Pro00039569 NCT01884545

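### At 12 months the plan lets HbA1c be ordered in place of fasting glucose, the analysed outcome; the unmodelled age of the 12-month labs is a lesser, related gap

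*Combined protocol and SAP*

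**What the plan says.** Section 5.3.1 (12-month visit) lists fasting glucose and the lipid values as the results to document from the medical record. The coordinator looks before the visit ("CRC will check in EMR prior to each" participant's 12-month appointment). The fallback reads: "If lab values as stated above are not available from the last 6 months of study participation", then a lipid panel is ordered and "either a FBG or HbA1c will be ordered".

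Table 2 schedules these labs at baseline and 12 months only, and names fasting glucose. Aim 2 in Section 2 covers "clinical outcomes (fasting blood glucose (FBG), systolic blood pressure (SBP), body mass index (BMI" and further measures, including the Framingham and diabetes risk scores. The risk assessment in Section 5.3.2 also uses fasting glucose: "The SRA consists of: FBG, age, gender, BMI, total cholesterol, HDL, BP". Section 8.2 lists fasting blood glucose among the metabolic dependent variables, and its time variable takes the values 0, 3, 6 and 12 months.

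Section 5.3.1 also says that "statistical analyses will employ extended inclusion windows for study time-points". It gives as a reason "recent findings on the stability of metabolic clinical markers absent behavior change", and sets plus or minus "11 weeks for the 12 month survey".

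**The concern.** The fallback does not cure the gap that triggers it. It applies when a recent fasting glucose (or lipid panel) is missing, yet it can be satisfied by an HbA1c, which leaves fasting glucose missing. Accepting either test makes sense for eligibility. It does not fit an outcome draw when only one of the two tests is analysed. With a single post-baseline laboratory time point, no later value can replace the lost one.

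The same choice exists at baseline (Sections 3.2 and 5.3.1), so FBG can be missing at either end. A participant with HbA1c alone at both times adds nothing to the FBG analysis.

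The second, lesser matter is timing. A result labelled 12 months may come from any draw in the six months before the final visit. If intervention effects on labs change over that period, the month-12 effect is misestimated. This reaches FBG and the lipids, and also the two risk scores where they use those labs.

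**Working it through.** **1. Test needed against test ordered**

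| Place | Glycaemic measure |
|---|---|
| Section 2, Aim 2 | FBG |
| Section 5.3.1, 12-month values to document | fasting glucose |
| Table 2, 12 months | fasting glucose |
| Section 5.3.2, risk assessment | FBG |
| Section 8.2, dependent variables | FBG |
| Section 5.3.1, 12-month order if labs are missing | FBG or HbA1c |
| Sections 3.2 and 5.3.1, baseline | FBG or HbA1c |

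HbA1c is never listed as an analysed outcome, and no conversion or missing-data rule connects it to FBG.

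**2. Cost of a missing 12-month FBG (illustration)**

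The plan gives no figure to reproduce. Inputs:
- ρ = 0.35, the within-person correlation in Section 8.1, assumed to hold for FBG.
- q, the share without a 12-month FBG: 10% or 25%, both assumed.
- Missingness at random and equal across groups; baseline FBG present for all; unit variance at both times.

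In a two-time mixed model, a participant with baseline only still contributes through the correlation. Per participant in a group:
- Complete data: variance of the change = 2(1 − ρ) = 2 × 0.65 = 1.30.
- With share q missing: 1.30 + [q/(1 − q)](1 − ρ²), where 1 − ρ² = 0.8775.
- q = 0.10: 1.30 + 0.1111 × 0.8775 = 1.3975; ratio 1.3975/1.30 = 1.075.
- q = 0.25: 1.30 + 0.3333 × 0.8775 = 1.5925; ratio 1.5925/1.30 = 1.225.

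| q | Variance ratio | Standard error | Effective sample | Out of 212.5 |
|---|---|---|---|---|
| 10% | 1.075 | +3.7% | 1/1.075 = 0.930 | 197.7 |
| 25% | 1.225 | +10.7% | 1/1.225 = 0.816 | 173.5 |

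The 212.5 is 250 enrolled (Section 5.1) × 0.85 retained (Section 8.1).

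The ratio simplifies to 1 + [q/(1 − q)](1 + ρ)/2. Over correlations from 0 to 1 it runs from 1.056 to 1.111 at q = 10% (loss of 5% to 10%), and from 1.167 to 1.333 at q = 25% (loss of 14% to 25%). The result therefore depends far more on q than on ρ.

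**3. Which draw dates the look-back accepts**

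Six months is 26.1 weeks (4.348 weeks per month).

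| Final visit | Earliest accepted lab |
|---|---|
| Month 12 (week 52.2) | week 26.1, month 6.0 |
| Within the ±1 week visit window | month 5.8 to 6.2 |
| 11 weeks early (week 41.2) | week 15.1, month 3.5 |
| 11 weeks late (week 63.2) | week 37.1, month 8.5 |

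For an on-time visit, accepted draws run from about month 6 to month 12. For a late visit they can fall after month 12.

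**4. Look-back against analysis window**

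If the ±11-week window also governs labs, and the visit is exactly at 12 months, the look-back accepts draws from about weeks 26 to 41 that the analysis would exclude. Their presence on file also means that no new test is ordered. If the window covers surveys only, as it is worded, this conflict does not arise, and labs have no stated analysis window.

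**The case against.** Loss of FBG needs two things: no recent fasting glucose on file, and HbA1c chosen at ordering. Section 5.3.1 and Table 2 both name fasting glucose at 12 months, so sites may usually order it, and the 10% and 25% have no source. This stands as a limit on size. It does not remove the mismatch, because the rule as written permits the loss.

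On timing, taking labs from annual visits is a declared, practical choice (Section 5). The rule is the same in all four groups and creates no effect under the null. SBP, BMI and waist are measured in the clinic at 12 months. The case report form is not in the documents and may record draw dates; the coordinator needs the date to apply the six-month rule. Section 8.2 leaves the form of the longitudinal model open, so nominal coding of labs is an inference. All of this stands, and it makes timing a minor point.

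Three stronger readings are tempting and not supported:
- A reader might infer from the pattern 2 means in Section 8.1 (coaching difference 1.375 at 6 months, 0.80 at 12) that early labs would exaggerate the month-12 laboratory effect. Those are standardized planning means for health behaviours. The documents give no laboratory trajectory; effects could fade, plateau or build late.
- A reader might infer that a record-based lab can only be early. It precedes the visit, but the visit itself may be late.
- A reader might infer that 15/26 = 58% of accepted labs fall outside the analysis window. That is a share of look-back weeks, not of labs. It needs a visit exactly at week 52 and a window that applies to labs, which the text does not state.

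**Conclusion.** The mismatch between the ordered test and the analysed outcome is in the text and should be corrected. The plan allows the only post-baseline FBG to be lost on a draw that happens anyway. The 7% and 18% losses of effective sample illustrate the cost under the stated assumptions; they do not estimate what will happen in this trial.

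The timing gap is real but minor. If laboratory effects change between months 6 and 12, the month-12 effect is misestimated in an unknown direction. No percentage for labs can be derived from the documents. The conflict between the look-back and the 11-week window is conditional on how that window is read.

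**What to change.** 1. **Ordered test.** In the 12-month paragraph of Section 5.3.1, order FBG, with HbA1c optional. Where labs are drawn for the study at baseline because none are on file (Section 3.2), include FBG there too. The cost is that fasting is required for that draw; no extra draw is needed. Participants who enter with only an HbA1c on file would still lack a baseline FBG.

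2. **Draw date.** Confirm that laboratory draw dates are recorded. Add to Section 8.2 a sensitivity analysis using actual time since randomization for FBG, LDL, triglycerides, total cholesterol and the two risk scores. The cost is at most one date field and one further set of models. An analysis restricted to draws near month 12 is optional; it loses precision and selects on post-randomization laboratory timing.

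3. **Window.** State whether the ±11-week window also governs labs. If it does, reconcile it with the six-month look-back by saying how an accepted but out-of-window lab is handled. This is a wording change.

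The use of annual-visit labs can stay.
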